Even where flucytosine (5FC) is available, it is often not administered because of overstated fears regarding toxicity (Loyse et al., 2013). The most serious drug-related adverse effect of 5FC is bone marrow suppression and hepatotoxicity (Vermes et al., 2000). In California's study, 5FC had been discontinued in over half of the patients because of cytopenia (Chuck & Sande, 1989). One patient in South Africa study also was discontinued 5FC because of thrombocytopenia on day-4 and the regimen was switched early to fluconazole (Bicanic et al., 2008). And also grade-4 neutropenia was recorded in 3.2% of the patients with 5FC (Molloy et al., 2018). But

in Thailand study, the treatment was well tolerated and there was no severe bone-marrow depression with 5FC (Brouwer et al., 2004).

Regarding amphotericin B Deoxycholate, its major drug-related adverse effects include nephrotoxicity and anemia (Bicanic et al., 2015). In Vietnam trial, Grade 3 and 4 anaemia were most prominent between amphotericin B plus flucytosine (35%) and amphotericin B plus fluconazole group (29%) (Day et al., 2013). Renal impairment occurs in nearly all patients treated with clinically significant doses of amphotericin. Fluconazole is relatively nontoxic, but reported to cause abnormalities in liver enzymes and very rarely, clinical hepatitis (Lampiris & Maddox, 2018).

Although WHO treatment guidelines recommend treatment regimen containing flucytosine as the preferred therapy, in clinical practice, treatment is highly variable due to drug costs, availability, and ability to monitor and manage drug-related toxicities (Perfect, 2010). A previous study was carried out in Mandalay for cryptococcal meningitis with fluconazole monotherapy by Than-Maung in 2006 and amphotericin B monotherapy by Myo-Thet-Naing in 2013 but the effectiveness and safety of amphotericin with flucytosine and fluconazole combination regime have not been studied in Myanmar. Thus, this study will provide information regarding the clinical effectiveness and safety of this treatment regimen for management of HIV-associated cryptococcal meningitis in Myanmar.

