### **2.1.11. Preventing, monitoring and managing antifungal toxicity**

#### Preventing, monitoring and managing antifungal amphotericin B toxicity

Drug toxicity and side-effects from amphotericin B therapy, especially hypokalaemia, nephrotoxicity and anaemia, are barriers to optimal induction treatment, safe administration of amphotericin B should be given priority and may require referral to a centre with access to a minimum package of preventing, monitoring and managing toxicity (WHO, 2018).

Table 3. Minimum package for preventing, monitoring and managing amphotericin B toxicity (WHO, 2018).

Pre-emptive hydration and electrolyte supplementation	
Adults and adolescents	One litre of normal saline solution with 20 mEq of potassium chloride (KCl) over two hours before each controlled infusion of amphotericin B and one to two 8-mEq KCl tablets orally twice daily. An additional 8-mEq KCl tablet twice daily may

	be added during the second week. If available, magnesium supplementation should also be provided (two 250-mg tablets of magnesium trisilicate or glycerophosphate twice daily, or magnesium chloride 4 mEq twice daily).
Monitoring (adults, adolescents and children)	
Serum potassium	Baseline and 2–3 times weekly (especially in the second week of amphotericin B administration)
Serum creatinine	Baseline and 2–3 times weekly (especially in the second week of amphotericin B administration)
Haemoglobin	Baseline and weekly
Management (adults, adolescents and children)	
Hypokalaemia	If hypokalaemia is significant ( $K <3.3$ mol/l), increase potassium supplementation to 40 mEq KCl by intravenous infusion and/or one to two 8-mEq KCl tablets orally three times daily. Monitor potassium daily.
Elevated creatinine	If creatinine increases by $\geq 2$ fold from the baseline value, increase pre-hydration to 1 L every eight hours and consider temporarily omitting a dose of amphotericin B. Once creatinine improves, restart amphotericin B at 0.7 mg/ kg/day and consider alternate-day amphotericin B. If creatinine continues to rise, consider discontinuing amphotericin B and continuing with fluconazole at 1200 mg/ day, especially if seven doses of amphotericin have been received. Consider fluconazole dose adjustment if significant renal impairment. Monitor creatinine daily.

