Severe anaemia	Transfusion should be undertaken if possible for severe amphotericin B–related anaemia (anaemia may also be a reason to discontinue amphotericin B prematurely in the second week of a planned two-week induction course of amphotericin B with fluconazole)
Additional notes:	

- Potassium replacement should not be given to people with pre-existing renal impairment or hyperkalaemia.
- Careful attention should be given to monitoring of intake and output of fluid and daily weight, especially among children.
- Flucytosine – because of concerns about bone marrow suppression, regular monitoring of full blood counts should be considered.
- The incidence of renal dysfunction and electrolyte disturbance is much less with liposomal amphotericin preparations, but renal function and electrolytes still need to be monitored

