### **2.1.12. Safety**

In ACTA trial, they randomly assigned HIV-infected adults with cryptococcal meningitis to receive an oral regimen (fluconazole [1200 mg per day] plus

flucytosine [100 mg per kilogram of body weight per day] for 2 weeks), 1 week of amphotericin B (1 mg per kilogram per day), or 2 weeks of amphotericin B (1 mg per kilogram per day). Each patient assigned to receive amphotericin B was also randomly assigned to receive fluconazole or flucytosine as a partner drug. Laboratory-defined side effects were less frequent in the oral-regimen group than in the 1-week or 2-week amphotericin B groups. Grade 4 anemia developed in 0.9% of patients in the oral-regimen group, 4.9% of patients in 1-week amphotericin B groups, and 8.8% of patients in the 2-week amphotericin B group. And also Grade 3 anemia developed in 4% of patients in the oral-regimen group, 8.9% of patients in 1-week amphotericin B groups, and 17.5% of patients in the 2-week amphotericin B group. A grade 3 or 4 increase in the serum creatinine level developed in 4.9% of patients in the oral-regimen group, 6.2% of patients in the 1-week amphotericin B groups, and 8.8% of patients in the 2-week amphotericin B groups. Grade 4 hypokalemia developed in only one patient, most likely because preemptive electrolyte replacement was provided for patients receiving amphotericin B.

Grade 4 neutropenia was recorded in 3.2% of the patients who were taking a regimen that included 2 weeks of flucytosine, in 0.9% of those taking 1 week of flucytosine, and in 1.3% of those taking a flucytosine free regimen. A grade 4 increase in the alanine aminotransferase level developed in only two patients, one of whom was taking fluconazole. Clinical adverse events were frequent with all regimens, which was reflective of the severe immunosuppression in this patient population.

As a partner drug with amphotericin, 1week amphotericin and flucytosine group develop Grade 3 and 4 anaemia of 8.8% and 24.56 % in 2 weeks amphotericin and fluconazole group. (Molloy et al., 2018).

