###### **(ii) Fever**

It is defined as rise in body temperature above 37 °C (98.6 °F) in the morning.

(iii) Convulsion

It is defined as a medical condition where body muscles contract and relax rapidly and repeatedly, resulting in uncontrolled actions of the body.

(iv) Abnormal mental status

It is defined as patients is somnolent, lethargy, disoriented and disruptions in perception and behavior.

(4) Clinical safety

Clinical safety will be assessed by laboratory defined adverse events. Adverse event is defined as any untoward medical occurrence in a subject to whom a medicinal product has been administered including occurrences which are not necessarily caused by or related to that product (Division of AIDS, 2017). Laboratory parameters (hematological and biochemical parameters) such as HGB, NEUT, PLT, ALT, AST, serum creatinine, serum potassium level will be graded according to DAIDS grading in appendix 3. Bone marrow suppression is defined as Grade 3 and 4 adverse events in one or more of anaemia, neutropenia and thrombocytopenia.

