#### 4.12. Algorithm

## 5. DUMMY TABLES

Table 4. Number of Cryptococcal meningitis in patients with HIV infection enrolled from individual specialist hospital

Hospital	Number (N)	Percentage (%)
Specialist hospital Waibargi		
Specialist hospital Mingalardon		
Specialist hospital Thakeyta		
Total		

Table 5. Distribution of age among study group of Cryptococcal meningitis in patients with HIV infection

Age (completed years)	Amphotericin B, Flucytosine plus Fluconazole group	
	Number	Percentage
≤20		
21-40		
>40		
Total		

Table 6. Distribution of gender among study group of Cryptococcal meningitis in patients with HIV infection

Gender	Amphotericin B, Flucytosine plus Fluconazole group	
	Number	Percentage
Male		
Female		
Total		

Table 7. Frequency distribution of headache among study group by Numerical rating Scale at day-1, day-7 and day-14

Days	Headache	Amphotericin B, Flucytosine plus Fluconazole group	
		Number	Percentage
day-1	No pain		
	Mild		
	Moderate		
	Severe		
	Intolerable		
Day-7	No pain		
	Mild		
	Moderate		
	Severe		
	Intolerable		
Day-14	No pain		
	Mild		
	Moderate		
	Severe		
	Intolerable		

Table 8. Clinical effectiveness of study group by assessing presence of headache, fever, convulsion, abnormal mental status and death at day-1, day-7 and day-14

Clinical parameters	Amphotericin B, Flucytosine plus Fluconazole group					
	Day 1		Day 7		Day 14	
	N	%	N	%	N	%
Headache						
Fever						
Convulsion						
Abnormal mental status						
Death						

Table 9. Laboratory-defined adverse events of amphotericin B, flucytosine and fluconazole at baseline and day-7 and day-14 by DAIDS grading

Days	DAIDS Grading	Hematological parameters & Biochemical parameters								Total
		Anaemia N (%)	Neutropenia N (%)	Thrombocytopenia N (%)	Elevated ALT level N (%)	Elevated AST level N (%)	Hypokalemia N (%)	Hyper creatinemia N (%)		
Baseline	Grade 1									
	Grade 2									
	Grade 3									
	Grade 4									
Day-7	Grade 1									
	Grade 2									
	Grade 3									
	Grade 4									
Day-14	Grade 1									
	Grade 2									
	Grade 3									
	Grade 4									

Table 10. Proportion of patients with grade 3 and 4 adverse events of hematological parameters at baseline, day-7 and day-14

	Grade 3 and 4 adverse events	Baseline		Day -7		Day -14	

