## VIII. Assessment of Convulsion

Days	Convulsion	
	Present	Absent
Day 1		
Day 7		
Day 14		

IX. Assessment of Abnormal mental status

Days	Abnormal mental status	
	Present	Absent
Day 1		
Day 7		
Day 14		

X. Laboratory (hematological and biochemical) parameters

hematological and biochemical parameters	Baseline	Day-7	Day-14
HGB (g/dL)			
NEUT ( $10^3/\mu\text{L}$ )			
PLT ( $10^3/\mu\text{L}$ )			
ALT (U/L)			
AST (U/L)			
Serum creatinine ( $\mu\text{mol/L}$ )			
Potassium (mmol/L)			

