**Division of AIDS (DAIDS) Table for Grading the Severity of Adult and Pediatric Adverse Events**

Parameter	Grade 1 Mild	Grade 2 Moderate	Grade 3 Severe	Grade 4 Potentially life- threatening
Hemoglobin, Low (g/dL) $\geq$ 13 years of age (male only)	10.0 - 10.9	9.0 - 10.0	7.0 - 9.0	< 7.0
$\geq$ 13 years of age (female only)	9.5 - 10.4	8.5 - 9.5	6.5 -8.5	< 6.5
Absolute Neutrophil Count (ANC), Low (cells/L)	0.800-1.000 x $10^9$	0.600-0.799 $x 10^9$	0.400-0.599 $x 10^9$	< 0.400 x $10^9$
Platelets, Decreased (cells/L)	100-125 x $10^9$	50-100 x $10^9$	25- 50 x $10^9$	< 25 x $10^9$
ALT or SGPT, High Report only one	1.25-2.5 ULN	2.5-5.0x ULN	5.0 - 10.0 x ULN	$\geq$ 10.0 x ULN
AST or SGOT, High Report only one	1.25-2.5 x ULN	2.5 - 5.0 x ULN	5.0 -10.0 x ULN	$\geq$ 10.0 x ULN
Creatinine, High	1.1-1.3 x ULN	> 1.3 -1.8 x ULN OR Increase to 1.3 - 1.5 x participant's baseline	> 1.8 - 3.5 x ULN OR Increase to 1.5 to < 2.0 x participant's baseline	$\geq$ 3.5 x ULN OR Increase of $\geq$ 2.0 x participant's baseline
Potassium, Low (mEq/L; mmol/L)	3.0 -3.4	2.5 - 3.0	2.0- 2.5	< 2.0
	3.0 -3.4	2.5- 3.0	2.0 -2.5	< 2.0

**Normal range of laboratory (hematological and biochemical) parameters in  
SHW, SHM and SHT**

Hematological and biochemical parameters	Normal Range
HGB (g/dL)	11-16
NEUT ( $10^3/\mu\text{L}$ )	2-7.5
PLT ( $10^3/\mu\text{L}$ )	150-400
ALT (U/L)	10-60
AST (U/L)	10-50
Serum creatinine ( $\mu\text{mol/L}$ )	53.0-114.9
Potassium (mmol/L)	3.5-5.5

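### Serum potassium is collected in both directions but graded and tabulated only when low, so a value above the sites' upper limit of 5.5 mmol/L appears in no planned table

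*Combined protocol and SAP*

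**What the plan says.** Objective 4 (Section 3.2) is to describe safety through haematological and biochemical parameters, graded by DAIDS, at baseline, day 7 and day 14. Section 4.10, item (4), states: "Clinical safety will be assessed by laboratory defined adverse events". It names serum potassium among the parameters to be graded and defines an adverse event without requiring a causal link to the drug.

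The pro forma (Annex 1, item X) has a numeric potassium entry in mmol/L for all three visits. Annex 3 gives the sites' normal range as 3.5-5.5 mmol/L, but the only potassium row in its grading table is "Potassium, Low".

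In Section 5, Table 9 has one potassium column, "Hypokalemia N" (with percentage), followed by creatinine and a Total. Tables 10 and 11 cover haematology only. Section 4.9 says that the laboratory gradings will be summarised as numbers and percentages. It specifies no mean, range or out-of-range count for potassium.

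**The concern.** The plan collects a two-sided measurement, commits to grading it, and then provides categories for one side only. What is at stake is the completeness of the safety description in Objective 4, since laboratory-defined events are the only route by which safety is assessed.

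The documents give some reason to look at the high side. Section 1.1 says of amphotericin B deoxycholate that "its major drug-related adverse effects include nephrotoxicity and anemia", and adds that renal impairment is seen in nearly all patients given clinically significant doses. Pregnancy is the only exclusion (Section 4.6.2), so patients with impaired renal function or a raised potassium at entry can be enrolled. A reader of the finished Table 9 could not tell whether any patient had a high value.

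**Working it through.** **1. Where a potassium value goes under the plan.** The Annex 3 bands for low potassium (mmol/L) are grade 1, 3.0-3.4; grade 2, 2.5-3.0; grade 3, 2.0-2.5; grade 4, below 2.0. Applying them:

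| Potassium (mmol/L) | Against site range 3.5-5.5 | Grade | Table 9 cell |
|---|---|---|---|
| 1.9 | below | 4 | yes |
| 2.2 | below | 3 | yes |
| 2.7 | below | 2 | yes |
| 3.2 | below | 1 | yes |
| 3.5 to 5.5 | within | none | none |
| 5.6 | above | none | none |
| 6.5 | above | none | none |
| 8.0 | above | none | none |

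Every value above 5.5 is handled exactly as a normal value is.

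**2. Whether another output would show it.** Tables 7 and 8 are clinical, and Tables 10 and 11 are haematological. Section 4.8 says in general terms that biochemical parameters will be described, but Section 4.9 and the dummy tables turn that into graded counts only. No planned output shows a high potassium.

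**3. The plan's own sample size, as the denominator.** Section 4.7.1 uses n = z²p(1-p)/d².
- Safety: 1.96² × 0.83 × 0.17 / 0.14² = 27.66.
- Effectiveness: 1.96² × 0.80 × 0.20 / 0.15² = 27.32.

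The stated 27 is the rounded-down value; rounding up gives 28. Nothing here depends on the difference.

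**4. Weight of one patient.** 1/27 = 3.7%. The denominator will shrink if patients die or are not measured. As an illustration only, one study cited in Section 2.1.13 had 9 deaths among 63 patients at 2 weeks. The same fraction here would leave 27 × 54/63 ≈ 23 patients, and 1/23 = 4.3%.

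**5. Chance that the gap affects anyone.** The documents give no rate of high potassium, so the rates p below are assumptions. The chance of at least one such patient among 27 is 1 - (1 - p)^27:

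| Assumed rate | Chance of at least one |
|---|---|
| 1% | 24% |
| 2% | 42% |
| 5% | 75% |
| 10% | 94% |

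The spread shows that the documents cannot settle how often the gap would matter.

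**The case against.** The best defence is that low potassium is the toxicity the cited literature reports. Section 2.1.11 names hypokalaemia among the main amphotericin B toxicities, Sections 2.1.12 and its trial summaries report hypokalaemia, and no section reports a case or rate of treatment-related high potassium. Renal toxicity has its own graded creatinine column. The numeric values are on the form, so a count could be added at write-up with no loss of data. This explains the choice and limits the seriousness. It does not explain why values that are collected and listed for grading should have no place in the tables.

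Several stronger readings are tempting but not supported:

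- **That study patients are loaded with potassium.** Table 3 describes "One litre of normal saline solution with 20 mEq of potassium chloride (KCl) over two hours before each controlled infusion of amphotericin B", plus oral tablets. This is a WHO package reproduced in the literature review. Section 4.8 does not prescribe it, and Section 4.11 says only that care is routine. The package also carries a safeguard: "Potassium replacement should not be given to people with pre-existing renal impairment or hyperkalaemia". With amphotericin B given for one week, pre-infusion potassium under that package would have ended before day 14.
- **That the plan reports zero cases of high potassium.** Table 9 has no such cell and no row for patients without an event. The values are not tabulated, which differs from being counted as zero. The hypokalaemia percentages are not distorted.
- **That any value above 5.5 is dangerous or is drug toxicity.** The documents give 5.5 only as the upper limit of normal, and a high baseline value precedes treatment.
- **That a low hypokalaemia rate would be an artefact of the Table 3 package.** Section 2.1.12 says that grade 4 hypokalaemia was rare in the cited African trial "most likely because preemptive electrolyte replacement was provided for patients receiving amphotericin B". That remark concerns electrolyte replacement in another trial. It does not credit saline and gives no overall hypokalaemia rate.

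**Conclusion.** The point holds as a gap in reporting. Potassium above 5.5 mmol/L has no grade, no planned table and no place in Table 9's Total, although Section 4.10 lists potassium for grading and defines adverse events regardless of cause. The number of patients affected is unknown and may be none. Each would be about 3.7 percentage points if 27 are measured, and more if fewer are. The conclusion rests on Annex 3 and the dummy tables being the full set of planned laboratory outputs, which is how Section 4.9 reads.

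No sample size, test or comparison is affected. Bedside care is not in question either, since Section 4.11 has adverse reactions passed to the physician. This is a free improvement, not a defect that undermines the study.

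**What to change.** Add a high-potassium column to Table 9 giving the number and percentage of patients above the Annex 3 upper limit of 5.5 mmol/L at baseline, day 7 and day 14. Use the number with a potassium measurement at that visit as the denominator, and print that number. Include these events in the Total. Because the count is ungraded, enter it once per visit across the four grade rows and give the Total a visit-level figure. Baseline belongs in the column because Table 9 already shows baseline for the other parameters.

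Add grades for high potassium only if the source DAIDS table provides them. Annex 3 does not reproduce such a row, so its cut-offs would have to be checked at source.

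Optionally, pro forma section V, which lists only the three antifungals, could record from the chart whether preventive potassium and pre-infusion saline were given. That would help in reading the hypokalaemia rate, but the point does not depend on it.

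The cost of the main change is one column built from values already collected. It needs no new test, no extra patients and no clinical rule.

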### Annex 1. Pro forma

Title: Clinical effectiveness and safety of amphotericin B with flucytosine-fluconazole combination therapy for cryptococcal meningitis in patients with HIV infection.

Date -----

Study site -----

Code No -----

#### I. Personal Identification

IPD Registration No. -----

Name -----

Age -----

Gender       Male       Female

Date of Admission -----

Occupation -----

Address -----

#### II. History taking and physical examination

Time of diagnosis of HIV ----- days ----- months ----- years

ART status      Yes

No       Defaulter

CD4 count at admission ----- cells/ $\mu$ L

#### III. CSF Findings

##### Macroscopic

Colour -----

##### Microscopic

Total cells count

R.B.C. -----/cmm      Neutrophil -----%

W.B.C. -----/cmm      Lymphocyte -----%

CSF glucose -----/mg/dL      CSF protein ----- mg%

India ink stain, Encapsulated yeast cell- seen       not seen

CSF opening pressure, cm H2O

Therapeutic lumbar puncture  mL

CSF Crypto Ag

Positive  negative 

## IV. Clinical diagnosis

-----

## V. Treatment

Amphotericin B	1 mg/kg	1 week
Flucytosine	100 mg/kg	
Fluconazole	1200 mg/day	1 week

## VI. Assessment of Headache (Headache Severity by Numerical rating scale)

Days	Numerical rating Scale				
	No pain 0	Mild 1-3	Moderate 4-6	Severe 7-9	Intolerable 10
Day 1					
Day 7					
Day 14					

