#### **3.2. Objectives**

1. To find out the back-ground characteristics of patients with HIV-associated cryptococcal meningitis
2. To describe the clinical effectiveness of amphotericin B with flucytosine-fluconazole combination therapy by assessing clinical parameters at day 1, day 7 and day 14
3. To determine the severity of headache before and after treatment by numerical rating scale
4. To describe the clinical safety of amphotericin B with flucytosine-fluconazole combination therapy by assessing hematological and biochemical parameters by DAIDS grading at baseline, day 7 and day 14

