#### **4.9. Data Management and Analysis**

Data will be collected by using pre-constructed pro forma. Following data collection and prior to data entry, all data will be carefully screened for accuracy.

Data entry will be done by using Microsoft Excel 2019. The data will be statistically analyzed by using computerized statistical software SPSS (Statistical Package for Social Science Version 21).

Data summarization for description will be done by showing frequency distribution tables and appropriate graphs. The parameters for clinical effectiveness and laboratory-defined adverse event gradings will be described by number, percentage in treatment group.

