###### **(i) Severity of headache**

Severity of headache is assessed by using Numerical rating scale (NRS). The NRS score range from zero to 10. Headache severity will be categorized according to the number given by patients for their headache. Headache will be categorized as no pain, mild, moderate, severe, and intolerable when scores are 0, 1-3, 4-6, 7-9, and 10. Headache will be evaluated by administration of a headache questionnaire at day-1, day-7 and day-14.

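### The pro forma has no field for the 0-10 headache score that patients give, so the before-after comparison in objective 3 is coarser than the data already being asked for

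*Combined protocol and SAP*

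**What the plan says.** Objective 3 in section 3.2 is: "To determine the severity of headache before and after treatment by numerical rating scale".

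Section 4.10, under severity of headache, sets the scale: "The NRS score range from zero to 10". It derives the category from the patient's own number: "Headache severity will be categorized according to the number given by patients for their headache". The cut-points follow: "Headache will be categorized as no pain, mild, moderate, severe, and intolerable when scores are 0, 1-3, 4-6, 7-9, and 10". Annex 3 repeats these rules and prints a 0-10 number line on which the patient picks a value.

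Section 4.9 names the collection tool: "Data will be collected by using pre-constructed pro forma". In Annex 1, section VI of that form, "Assessment of Headache (Headache Severity by Numerical rating scale)", has a row for each of days 1, 7 and 14 and a column for each of the five bands. It has no field for the number.

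The planned output is "Table 7. Frequency distribution of headache among study group by Numerical rating Scale at day-1, day-7 and day-14", which gives number and percentage per band per day. Table 8 adds only whether headache is present. No summary of the score and no within-patient change is planned.

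**The concern.** Objective 3 is a before-after question about severity, and the patient is already asked for an 11-level answer. The form named for data collection has room for only five levels. A change within a band therefore does not show, and a change across a band boundary shows as one step whatever its size in points. If the number never reaches the data set, the analysis can report shifts between bands but not how many points a patient's headache fell. Nor could a definition of change in points be applied to that data set later.

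The same form already handles laboratory results the other way round. Section X records raw values such as haemoglobin and creatinine, which are graded afterwards with the DAIDS table in Annex 3. Headache is the exception.

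**Working it through.** **The plan's own figure.** The effectiveness sample size in section 4.7.1 uses n = z²p(1−p)/d² with z = 1.96, p = 0.8 and d = 0.15:

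n = 3.8416 × 0.8 × 0.2 / 0.0225 = 27.32.

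The plan states 27. The half-width at n = 27 is 1.96 × √(0.8 × 0.2 / 27) = 0.151, so the planned precision is met to rounding. The calculation rests on a proportion and does not use the 0-10 score, so nothing below changes it.

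**Inputs for the check.** The scale runs from 0 to 10 (section 4.10 and Annex 3). The bands are 0, 1-3, 4-6, 7-9 and 10 (section 4.10, Annex 1 section VI and Annex 3).

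**Step 1: count the possible falls.** With 11 scores there are 11 × 10 / 2 = 55 pairs in which the later score is lower.

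**Step 2: count the falls that stay within a band.** A one-score band contains none. A three-score band contains 3: two of one point and one of two points. Three such bands give 3 × 3 = 9.

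| Size of fall | Possible | Band unchanged | Band changes |
|---|---|---|---|
| 1 point | 10 | 6 (9→8, 8→7, 6→5, 5→4, 3→2, 2→1) | 4 (10→9, 7→6, 4→3, 1→0) |
| 2 points | 9 | 3 (9→7, 6→4, 3→1) | 6 |
| 3 points or more | 36 | 0 | 36 |
| All | 55 | 9 | 46 |

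So a fall from 9 to 7 leaves the patient in the severe band, while a fall from 7 to 6 moves the patient from severe to moderate.

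**Step 3: what a one-band drop can mean.**

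| Drop | Smallest fall | Largest fall |
|---|---|---|
| Intolerable to severe | 10→9 = 1 | 10→7 = 3 |
| Severe to moderate | 7→6 = 1 | 9→4 = 5 |
| Moderate to mild | 4→3 = 1 | 6→1 = 5 |
| Mild to no pain | 1→0 = 1 | 3→0 = 3 |

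**Step 4: with the number recorded.** All 55 falls are distinguishable from no change, against 46 of 55 with bands alone, and the size of each fall is known.

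**The case against.** The strongest reply is that the plan is coherent as it stands. The study is descriptive, section 4.9 promises numbers and percentages, the bands are prespecified and identical wherever they appear, and section VI supplies everything that Table 7 needs. Objective 3 does not mention change in points, and no threshold is given that would make a change of 1 or 2 points important. All of this stands. It limits the point to an improvement and does not show an error in the planned tables. Within-patient shifts between bands would also remain available from the form.

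A reader might go further in four ways that the documents do not support.

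- **That the score is irrecoverably lost.** Section 4.10 describes a headache questionnaire at each time point, section 4.8 says severity is documented with the scale, and Annex 3 holds the 0-10 line. The number may survive on that sheet. Nothing says that the sheet is discarded, but nothing says that it is kept or entered either. The supportable statement is that the collection form has no field for it.
- **That the form allows only a mark in a band.** The cells in section VI are blank. A number could be written in one, although nothing asks for it.
- **That the unequal band widths cause the problem.** All 9 hidden falls lie inside the three bands of equal width, and the one-score end bands hide nothing. The cause is that bands span more than one score, and equal bands would do the same.
- **That the sample size is undermined.** It is not. Section 4.7.1 does rest on a proportion with headache improvement, and the protocol does not define improvement, but that is a separate matter which recording the number would not settle by itself.

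**Conclusion.** The point holds as a free improvement. The form keeps five levels of an answer that is given on eleven. As a result, 9 of 55 possible falls, all of 1 or 2 points, cannot be told from no change, and a drop between adjacent middle bands can stand for 1 to 5 points. Every fall of 3 points or more changes band.

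The conclusion rests on two things: the bands as printed, and the absence of any instruction to keep or enter the Annex 3 number. If the sites already enter that number, the remaining gap is only that no summary of it is planned. The counts describe what is possible on the scale. How often such falls would occur in about 27 patients cannot be said from the documents. Table 7 and the stated sample size are unaffected.

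**What to change.** In Annex 1 section VI, replace the five band columns with one box per day (1, 7 and 14) for the 0-10 number, and derive the bands at analysis from the existing cut-points. Keep Table 7 as it is. Add two summaries beside it:

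- the median (IQR) score at each day, with the number of patients scored;
- the within-patient change in points from day 1 to day 7 and from day 1 to day 14, among patients scored at both times, with that number stated so that patients who died or could not give a score are not silently dropped.

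The cost is an edit to one table of the form and a few summary rows. The number is already asked of the patient, so there is no new assessment, visit or burden, and the sample size does not change.
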